Vital signs and body weight, 12-lead ECG parameters, laboratory data (hematology, biochemistry, coagulation, urinalysis) will be summarized using descriptive statistics. Shift tables showing changes from baseline will be generated where appropriate.

Efficacy parameters:

Efficacy will be determined from the number of subjects with complete response, partial response, stable disease or progressive disease, according to iRECIST based on the investigator's assessments. PFS (percentage of subjects alive and progression-free after trial treatment start) will also be determined. These clinical response data will be summarized.

ORR (proportion of subjects with a best overall response of PR or, CR) will be evaluated based on iRECIST.

- For Phase I Cohort 3 and all Phase IIa arms, ORR (proportion of subjects with a best overall response of PR or, CR) will be evaluated by two additional approaches based on itRECIST:Injected response: considering only the targeted-injected lesions.
- Non-injected response: considering only the targeted-non-injected lesions.

Pharmacokinetic parameters:

Subjects who have received CyPep-1 and have provided one evaluable pre-dose and at least one post-dose PK blood sample will be evaluable for PK.

Standard methodology will be used to estimate PK parameters. Concentration-time profiles will be derived for subjects with pre- and post-dose samples.

Immunological parameters:

The relative changes in CD8+ T-cell infiltration (CD8+ expression) in the biopsied injected, and whenever available, non-injected lesion(s) between screening and Week 6 will be assessed.

The association between the relative changes in CD8+ T-cell infiltration and response rate in the injected lesions (per itRECIST) and all lesions (per iRECIST) will be assessed.

The change in T-cell receptor (TCR) clonality levels will be assessed in the available peripheral blood samples. To assess the hypothesis that CyPep-1 increases the TCR clonality systematically, which suggests that T-cells are targeting the tumor, the clonality diversity metric will be computed for all subjects providing peripheral blood samples at screening and/or Week 6 of every CyPep-1 treatment cycle. Based on preliminary on file data of TCR clonality analysis in peripheral blood dated Nov 2022, the dataset collected is sufficient for the intended analysis and further sampling will provide no additional insights. Uncertainty about the representativeness of data generated with blood samples regarding TCR changes in the tumor microenvironment has lead Cytovation to reconsider this scientific relevance of this assay. Therefore, Cytovation decided to stop collecting blood samples for TCR clonality analysis for all subjects. TCR sequencing might be performed on the available remaining tumor biopsy material from the analyses of changes in the tumor microenvironment. Overlaps of T cell clones in respect to expansion and breadth of T cell clonality before and after intratumoral injection with CyPep-1, as monotherapy and in combination with pembrolizumab (central analysis) will be analyzed.

The change in tumor microenvironment is examined via the expression of selected candidate immune markers by immunohistochemistry. For each marker, a difference in expression will be explored.

Changes in cytokine levels and in frequency of various immune cell types in peripheral blood (immunophenotyping) will be explored.

SCHEDULE OF ASSESSMENTS

The schedule of all assessments performed within the context of this clinical trial is provided in Tables 1a to 1d.

Table 1. Schedule of Assessments

Table 1a. Schedule of Assessments Phase I Dose Escalation and Phase IIa Arms A and C for Cycle 1 (CyPep-1 Monotherapy)

	Screening ¹	DLT observation period			Continued Treatment	EoT ²	FU ³	PFS-FU ⁴	OS-FU ⁵
Week	1	3	5	6					
Day	-28 to 1	D1	D15	D29	D36				Every 3 months
Visit no.	Screening	C1V1	C1V2	C1V3	C1V4				
Visit window	NA	-	± 3 d	± 3 d	± 3 d	± 3 d	-	-	-
Informed consent	X					See Table 1b			
Demography	X					Subsequent cycles ⁶			
Medical and surgical history ⁷	X								
Eligibility	X	X							
Tumor biopsy ⁸	X				X ²⁸				
Performance (ECOG) status ⁹	X	X	X	X	X	X	X	X	X
Height ⁹	X								
Weight ⁹	X	X	X	X	X	X	X	X	X
Physical examination ⁹	X	X	X	X	X	X	X	X	X
Vital signs ¹⁰	X	PRE- & 15m, 30m, 1h, 2h, 4h POST-dose	PRE- & 15m, 30m, 1h, 2h, 4h POST-dose	PRE- & 15m, 30m, 1h, 2h, 4h POST-dose	X	X	X	X	X
Electrocardiogram ¹¹	X	X	X	X	X				
Hematology and biochemistry ¹²	X	X	X	X	X	X	X	X	X

	Screening ¹	DLT observation period					Continued Treatment	EoT ²	FU ³	PFS-FU ⁴	OS-FU ⁵
Week	1	3	5	6							
Day	-28 to 1	D1	D15	D29	D36						
Visit no.	Screening	C1V1	C1V2	C1V3	C1V4						
Visit window	NA	-	± 3 d	± 3 d	± 3 d						
Creatinine clearance ¹³	X										
Coagulation ¹²	X	X	X	X							
Urinalysis ¹²	X	X	X	X							
Pregnancy test ¹⁴	X	X	X	X							
PK (first 9 subjects Phase I + all subjects Arm C) ¹⁵											
Cytokines ¹⁶	X		X								
Blood sampling for immune cell phenotyping ¹⁷	X		X								
Local measurement of tumor lesion(s) ¹⁸		X	X								
Administration of CyPep-1 ¹⁹		X	X	X							
Concomitant medication ²⁰	X	X	X	X							
AEs ²¹	X	X	X	X							
iRECIST assessment ²²											
Evaluation of survival and subsequent anti- cancer therapies											X

At 8-week (±3 days) intervals while on trial treatment²³

Table 1b. Schedule of Assessments Phase I Dose Escalation and Phase IIa Arms A and C (Starting Cycle 2 and all subsequent cycles monotherapy)²⁴

Week	1	3	5	6
Day	D1	D15	D29	D36
Visit no.	Cycle X Visit 1 ²⁵ (CXV1)	CXV2	CXV3	CXV4
Visit window	± 3 d	± 3 d	± 3 d	± 3 d
Weight	X			
Physical examination	X	X	X	
Vital signs ¹⁰	PRE- & 15m, 30m, 1h, 2h, 4h POST-dose	X	X	
Tumor biopsy	X ²⁶			X ²⁶
Performance (ECOG) status ⁹	X			
Hematology and biochemistry ¹²	X			
Urinalysis ¹²	X			
Pregnancy test ¹⁴	X	X	X	
Cytokines ¹⁶			X ²⁷	
Blood sampling for immune cell phenotyping ¹⁷			X	
Local measurement of tumor lesion(s) ¹⁸	X	X	X	
Administration of CyPep-1 ¹⁹	X	X	X	
Concomitant medication ²⁰	X	X	X	X
AEs ²¹	X	X	X	X
iRECIST assessment ²²				At 8-week (+3 day/s) intervals while on trial treatment ²³

Table 1c. Schedule of Assessments Phase IIa Arm B (Cycle 1 CyPep-1 plus pembrolizumab combination)

	Screening ¹	TLT observation period			Continued Treatment	EoT ²	FU ³	PFS-FU ⁴	OS-FU ⁵
Week	1	3	5	6					
Day	-28 to 1	D1	D15	D29	D36				
Visit no.	Screening	C1V1	C1V2	C1V3	C1V4				
Visit window	NA	-	± 3 d	± 3 d	± 3 d	± 3 d	± 1 wk	± 1 wk	± 1 wk
Informed consent	X								
Demography	X								
Medical and surgical history ⁷	X								
Eligibility	X								
Tumor biopsy ⁸	X					X ²⁸			
Performance (ECOG) status ⁹	X		X	X	X	X	X		
Height ⁹	X								
Weight ⁹	X	X	X	X	X	X	X	X	
Physical examination ⁹	X	X	X	X	X	X	X	X	X
Vital signs ¹⁰	X	PRE- & 15m, 30m, 1h, 2h, 4h POST-dose	PRE- & 15m, 30m, 1h, 2h, 4h POST-dose	PRE- & 15m, 30m, 1h, 2h, 4h POST-dose	PRE- & 15m, 30m, 1h, 2h, 4h POST-dose	X	X	X	X
Electrocardiogram ¹¹	X	X	X	X	X				
Hematology and biochemistry ¹²	X	X	X	X	X				
Creatinine clearance ¹³	X								
Coagulation ¹²	X	X	X	X	X				
Urinalysis ¹²	X	X	X	X	X			X	
Pregnancy test ¹⁴	X	X	X	X	X			X	
Cytokines ¹⁶	X					X			X

	Screening ¹	TLT observation period				Continued Treatment	EoT ²	FU ³	PFS-FU ⁴	OS-FU ⁵
Week	1	3	5	6						
Day	-28 to 1	D1	D15	D29	D36					
Visit no.	Screening	C1V1	C1V2	C1V3	C1V4					
Visit window	NA	-	± 3 d	± 3 d	± 3 d		± 3 d	± 1 wk	± 1 wk	± 1 wk
Blood sampling for immune cell phenotyping ¹⁷	X	X	X	X						
Local measurement of tumor lesion(s) ¹⁸	X	X	X	X						
Administration of CyPep-1 ¹⁹	X	X	X	X						
Administration of pembrolizumab ²⁹	X									
Thyroid function testing ³⁰	Every 6 weeks while on trial treatment									
Concomitant medication ²⁰	X	X	X	X			X	X		
AEs ²¹	X	X	X	X			X	X		
iRECIST assessment ²²						At 8-week (± 3 days) intervals while on trial treatment ²³				X
Evaluation of survival and subsequent anti-cancer therapies										X

Table 1d. Schedule of Assessments Phase IIa Arm B (Starting Cycle 2 and all subsequent cycles of CyPep-1 plus pembrolizumab combination)²³

Week	1	3	5	6
Day	D1	D15	D29	D36
Visit no.	Cycle X Visit X ²⁵ (CXV1)	CXV2	CXV3	CXV4
Visit window	± 3 d	± 3 d	± 3 d	± 3 d
Weight	X			
Physical examination	X	X	X	
Vital signs	PRE- & 15m, 30m, 1h, 2h, 4h POST-dose	X	X	
Electrocardiogram ¹¹	X			
Tumor biopsy	X ²⁶			X ²⁶
Performance (ECOG) status ⁹	X			
Hematology and biochemistry ¹²	X			
Urinalysis ¹²	X			
Pregnancy test ¹⁴	X	X	X	
Cytokines ¹⁶				X ²⁷
Blood sampling for immune cell phenotyping ¹⁷				X
Local measurement of tumor lesion(s) ¹⁸	X	X	X	
Administration of CyPep-1 ¹⁹	X	X	X	
Administration of pembrolizumab ²⁹				Every 6 weeks starting C1V1
Thyroid function testing ³⁰				Every 6 weeks while on trial treatment
Concomitant medication ²⁰	X	X	X	X
AEs ²¹	X	X	X	X
iRECIST assessment ²²				At 8-week (±3 days) intervals while on trial treatment ²³

Table 1e. Schedule of Assessments Phase IIa Arm D (CyPep-1 Monotherapy)

	Screening ¹	Treatment			Continued Weekly Treatment until Week 16	Bi-weekly Treatment	EoT ²	FU ³	PFS-FU ⁴	OS-FU ⁵
Week		1	2	3	4 to 16	17 onwards	-	-	-	-
Day	-28 to 1	D1	D8	D15	D22 to D106	D113 onwards	-	-	-	Every 3 months
Visit no.	Screening	V1	V2	V3	VN	VN'	-	-	-	-
Visit window	NA	-	± 3 d	± 3 d	± 3 d	± 3 d	± 1 wk	± 1 wk	± 1 wk	± 1 wk
Informed consent	X									
Demography	X									
Medical and surgical history ⁷	X									
Eligibility	X	X								
Tumor biopsy ⁸	X				X ³¹					
Performance (ECOG) status ⁹	X	X	X	X		X ³²	X	X	X	X
Height ⁹	X									
Weight ⁹	X	X	X	X		X ³²	X	X		
Physical examination ⁹	X	X	X	X		X ³²	X	X	X	
Vital signs ¹⁰	X				PRE- & 15m, 30m, 1h, 2h, 4h POST-dose		X	X		
Electrocardiogram ¹¹	X	PRE- & 30 min POST-dose	PRE- & 30 min POST-dose	PRE- & 30 min POST-dose		X ³²				
Hematology and biochemistry ¹²	X	X		X		X ³²	X			
Creatinine clearance ¹³	X	X	X							
Coagulation ¹²	X	X	X	X		X ³²				

List of footnotes

1. Re-screening may be allowed on a case-by-case basis. In the case of out-of-range laboratory results during the screening period, a re-test may be allowed within the screening period. The investigator must contact the medical monitor to discuss each re-screening case.
2. The EoT visit will be done within 7 days after the subject is taken off CyPep-1.

3. The FU visit will occur at least 30 days after the last CyPep-1 or pembrolizumab (combination arm) administration (if the EoT visit occurs more than 30 days after the last treatment administration, the FU visit will be skipped).
4. For subjects who leave the trial early and do not receive any other anti-cancer therapy or any other investigational therapy, PFS visits should continue to be performed every 8 weeks (from D1) until occurrence of confirmed progressive disease (PD) or until start of any further line of anticancer treatment.
5. Every 3 months after confirmed PD and until the end of the trial, by phone call. In case of unconfirmed PD (iUPD) by iRECIST and subject has started further line of anti-cancer treatment, the first OS-FU visit will be done 90 days after the iUPD event occurred. Besides overall survival status, any next line of anti-cancer therapies, ORR and duration of response to next line anti-cancer therapies, and additional relevant information will be recorded. If necessary, patients may be contacted occasionally outside of this FU window, and data regarding next line anti-cancer therapies can be collected, retrospectively.
6. Additional cycles of CyPep-1 are planned with continued Q2W administration, please see [Table 1 b/e](#) for schedule of assessments (in this case, end of treatment [EoT], FU, PFS-FU, and OS-FU are relative to each cycle).
7. Medical history should include details of cancer onset, prior surgery and past cancer treatments.
8. **For Arms A, B and C:** Arrangements to be made for any tumor material to be sent for analysis are described in the laboratory manual. Tumor biopsies (should be available from at least one injected lesion at screening and at Week 6 of Cycle 1) will be taken from injected and, whenever available, non-injected lesions at screening. At Week 6 (± 1 day), the same lesion(s) has to be used for the biopsy sampling. No biopsy is to be taken if tumor is inaccessible, biopsy not in subject's best interest or thought to be dangerous or if subject declines to consent to biopsy. **For Arm D:** Tumor biopsy from at least one injected lesion at screening and at Week 6 is highly desired but not mandatory.
9. ECOG performance status assessment, height, weight, and physical examination may be done the day before CyPep-1 administration or pembrolizumab administration (if pembrolizumab administration day is different from CyPep-1 scheduled day) before dosing for logistical reasons.
10. For vital signs (blood pressure, pulse and temperature), a time window of ± 5 min is allowed. **For Arms A, B and C:** Vital signs before and 15 min, 30 min, 1 h, 2 h and 4 h after treatment will be recorded for all subjects during Cycle 1 on Days 1, 15, 29 and 36 (DL/T/LT period). For all subsequent cycles, vital signs will be recorded on Day 1 before and 15 min, 30 min, 1 h, 2 h and 4 h after treatment. For all other Days of each cycle, only before treatment and if abnormal to be followed up at the investigator's discretion. **For Arm D:** Vital signs before and 15 min, 30 min, 1 h, 2 h and 4 h after treatment will be recorded for all subjects on each dosing day. For subjects who have no clinically significant abnormality with vital signs reported during the first four doses of CyPep-1 (on V1 (D1), V2 (D8), V3 (D15) and V4 (D22)), vital signs will be recorded before and 15 min, 30 min, and 1 h after treatment on all the subsequent dosing days.
11. Single 12-lead ECG recordings will be taken pre-dose of CyPep-1 or pembrolizumab administration (if pembrolizumab administration day is different from CyPep-1 scheduled day). Subjects must be supine for approximately 10 minutes, before ECG collection and remain supine but awake during ECG procedure. **For Arm D:** ECG recordings will be performed both pre-dose and 30 minutes after CyPep-1 administration at screening, V1 (D1), V2 (D8), V3 (D15), and every 6 weeks from V4 (D22).
12. The safety laboratory includes hematology, biochemistry, coagulation, and urinalysis (performed by dipstick) to be performed pre-dose of CyPep-1 or pembrolizumab administration (if pembrolizumab administration day is different from CyPep-1 scheduled day). Laboratory values assessed during screening less than 72 hours before CyPep-1 administration do not need to be repeated at Visit 1. Further assessments may be performed up to 1 day prior to the visit in order to have the results (of at least Hb, WBC, platelets, PT-INR, and APTT) available on the visit day prior to CyPep-1 and/or pembrolizumab administration.
13. Creatinine clearance will be measured using CKD-EPI formula pre-dose of CyPep-1 administration or pembrolizumab administration. Assessment less than 72 hours before CyPep-1 administration do not need to be repeated at Visit 1.
14. Women of childbearing potential must have a highly sensitive negative pregnancy test at screening (serum). Pregnancy testing (highly sensitive urine/serum) should be performed before each administration of trial treatment for the duration of the trial and at EoT, with an exception for Arm D, where the frequency of pregnancy testing should be performed before each administration during the first three visits followed by every 4 weeks counting from V4 (D22), ± 3 days (see footnote 33).
15. PK assessment will be done at the following time-points: **For Phase I, and Arm C:** (up to 1 hour) pre-dose, and 15 min, 30 min, 1 hour, 2 hours, and 4 hours post-dose. **For Arm D:** (up to 1 hour) pre-dose, and 15 min, 30 min, and 1 hour post-dose. A time window of ± 5 min is allowed for the PK blood samples.

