The dose of pembrolizumab in combination with CyPep-1 in the combination arm will be 400 mg Q6W. Dosing of CyPep-1 will be aligned such that subjects will receive both pembrolizumab and the first dose of CyPep-1 on the same day (C1V1). After C1V1, pembrolizumab dosing will continue following a Q6W dosing scheme until 18 cycles, confirmed PD, unacceptable toxicity or consent withdrawal.

DOSE-MODIFICATION CRITERIA:

CyPep-1: No major toxicity is expected. There may be minor local toxicity or tumor ulceration due to the treatment procedure, which can be treated according to Standard of Care.

In case of toxicity, the administration of CyPep-1 may be delayed at the discretion of the investigator and is to be discussed with the medical monitor. Neither a dose reduction, nor intra-subject dose escalation of CyPep-1 is allowed.

Dose modification of pembrolizumab in Arm B will be according to the provided dose modification and toxicity management guidelines (refer to Section 5.3.6).

SAFETY ASSESSMENTS:

Safety will be assessed by means of physical examinations, body weight, vital signs, ECOG performance status, laboratory evaluations (hematology, biochemistry, coagulation, urinalysis), electrocardiograms (ECG), and recording of concurrent illness/therapy and adverse events (as defined by CTCAE v5.0). All assessments will be performed as indicated in the Schedule of Assessments ([SoA, Table 1](#)). Additional assessments may be performed as clinically indicated.

EFFICACY ASSESSMENTS:

Clinical efficacy of CyPep-1 monotherapy (Phase I dose escalation and Phase IIa Arms A, C, and D) and in combination with pembrolizumab (Phase IIa Arm B) will be measured by radiologic assessments (i.e., caliper, CT, MRI) every 8 weeks, starting from C1V1 for all phases and arms as baseline. The imaging modality must be the same for all efficacy measurements.

Radiologic assessments will be evaluated based on the investigator's assessments at the clinical sites according to the consensus guideline iRECIST ([Appendix D](#), based on modified

RECIST) and response (iCPD, iUPD, iSD, iPR, iCR) will be defined taking into account the total disease burden (as required per iRECIST using modified RECIST).

ORR in injected and non-injected lesions per itRECIST will be estimated by statistical programming using data collected from iRECIST assessments.

The following tumor lesion(s) will be followed-up for efficacy:

- One or more injected lesion(s) that are treated with CyPep-1 injection.

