3.1.2 Dose Limiting Toxicities / Treatment Limiting Toxicities

A DLT is defined by the occurrence of any of the following toxicities according to CTCAE v5.0 during treatment Cycle 1 and that are considered by the investigator to be possibly, probably, or definitely related to CyPep-1:

3. Any Grade ≥ 3 AEs of any etiology, except:
 - o Nausea, vomiting, or diarrhea will be considered a DLT only if it persists at Grade ≥ 3 for > 3 days despite adequate supportive care measures. At the investigator's discretion, subjects who experience nausea, vomiting, or diarrhea after receiving CyPep-1 may receive antiemetic or anti-diarrheal medication prior to subsequent doses of CyPep-1.
 - o Isolated laboratory abnormalities Grade ≥ 3 (not present at baseline) that resolve to Grade ≤ 1 in ≤ 7 days without clinical sequelae or need for therapeutic intervention.
 - o Fatigue Grade ≥ 3 for ≤ 7 days.
 - o For Phase I, Arms A and C:
 - Alanine amino transferase (ALAT) or Aspartate amino transferase (ASAT) toxicities:
 - ALAT or ASAT $> 5 \times$ upper limit of normal (ULN) ($> 7.5 \times$ ULN for subjects with liver metastases), unless greater than 14 days.
 - ALAT or ASAT $> 5 \times$ ULN ($> 7.5 \times$ ULN for subjects with liver metastases) accompanied by an elevation in total bilirubin of $> 2.5 \times$ ULN (not explained by obstruction), regardless of duration, will be considered a DLT.
4. Any other toxicity occurring at any time during the trial that in the view of the participating investigators and the medical monitor represents a clinically significant hazard to the subject.

All TLTs will be graded using NCI CTCAE v5.0 based on the investigator assessment. The TLT window of observation will be during Cycle 1.

The occurrence of any of the following toxicities during Cycle 1 will be considered a TLT, if assessed by the investigator to be possibly, probably, or definitely related to trial treatment administration.

1. Grade 4 nonhematologic toxicity (not laboratory).
2. Grade 4 hematologic toxicity lasting ≥ 7 days, except thrombocytopenia:
 - Grade 4 thrombocytopenia of any duration
 - Grade 3 thrombocytopenia associated with clinically significant bleeding

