5.3.1.1 CyPep-1 Dose Levels

For Phase I, in three dose cohorts of 3 subjects each, subjects received CyPep-1 intratumorally at different concentrations (dose escalation) and volumes (depending on tumor size), i.e., 0.5 mg/mL, 2 mg/mL, or 5 mg/mL, respectively.

The CyPep-1 concentration for each dose cohort of the dose escalation (Phase I) was as follows:

Dose cohort	CyPep-1 concentration
1	0.5 mg/mL
2	2 mg/mL
3	5 mg/mL

Subjects in Phase IIa expansion arms (Arms A, B and D) of the trial will be treated at the CyPep-1 RP2D dose determined in Phase I. Based on the review of all safety data for the three dose cohorts and recommendation by the DEC (dated 09 Sep 2021), a RP2D for CyPep-1 is 5.0 mg/mL to be taken forward in Phase IIa.

During the dose expansion in liver metastases (Arm C), the safety and tolerability of at least two dose levels of CyPep-1, the RP2D (cohort 5) and the dose immediately below that (cohort 4), are planned to be evaluated when CyPep-1 is administered intratumorally into 1 single lesion in the liver.

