5.3.4 Selection of CyPep-1 Doses in the Trial

In Phase I of the trial, CyPep-1 will be administered intratumorally in escalating doses as follows:

1. Cohort 1: 0.5 mg/mL on Day 1 of Weeks 1, 3, and 5 (Days 1, 15, and 29)
2. Cohort 2: 2 mg/mL on Day 1 of Weeks 1, 3, and 5 (Days 1, 15, and 29)
3. Cohort 3: 5 mg/mL on Day 1 of Weeks 1, 3, and 5 (Days 1, 15, and 29)

Continuous Q2W administration of CyPep-1 is planned after Day 29.

Selection of these doses was based on previous preclinical experience with CyPep-1 ([Szczepanski et al, 2014](#)). The total amount of CyPep-1 injected will depend on the tumor volume. The volume delivered to each lesion selected for injection will be determined based on the longest diameter measured by the most accurate measurement technique available for each lesion (e.g. caliper, CT, or MRI) at screening and every 8 weeks during the iRECIST/itRECIST assessments (see [Section 5.3.1.2](#)). Before each injection, the longest diameter of the lesion will be measured. The approximate injected volume per lesion will be 1 - 4 mL for lesions <1.5 cm, 2 - 4 mL for lesions ≤ 4 cm, 3 - 4 mL for lesions > 4 cm. Efforts should be made to administer the maximum volume of CyPep-1 per administration as per dose level.

For Phase IIa Arms A, B and C, weekly administration schedule for the first 6 weeks should be considered for a lesion > 7 cm followed by Q2W administration.

The proposed CyPep-1 starting dose for the clinical trial is obtained from the therapeutic range identified in the nonclinical in vitro (0.025 mg/mL) and *in vivo* intratumoral studies (1-5 mg/mL (refer to [IB](#)). The data suggests that the starting dose of 0.5 mg/mL in the tumor microenvironment is within the identified range to achieve an initial and meaningful biological effect. Since intravascular administration can occur during intratumoral injection, the NOEL from IV administration studies was considered relevant to identify the first dose. Based on the 7 days toxicology study of repeat IV bolus with CyPep-1, the NOEL of 3,0 mg/kg was identified in rats. The corresponding HED is 0,48 mg/kg (0.16 x 3,0 mg/kg). For a 70 kg person this equals 33.6 mg. As the maximal cumulative starting dose in trial is 2 mg, a safety factor of 16.8 has been taken into account, considering that the route of administration is intratumoral instead of IV with limited systemic exposure anticipated.

Planned doses in the trial:

- 2 mg/mL (cumulative 8 mg) and 5 mg/mL (cumulative 20 mg)

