- CICILIA Phase I dose escalation used IT administered CyPep-1 (comparable to subcutaneous administration study showing ~100-fold lower Cmax / ~20-fold lower AUC compared to IV with an ~ 5% bioavailability).
- AE summary of RP2D determined during Phase I: 5 mg/mL dose (20 mg CyPep-1) resulted in related TEAEs of injection site pain Grade 1 and 2 (AE number = 12) without DLTs, SAEs or AEs leading to discontinuation.

In Phase IIa of the trial, all subjects will receive intratumoral CyPep-1 at the doses specified in [Section 5.3.1](#).

Phase I, the dose escalation part of the CICILIA trial, has been completed. The determined RP2D of IT administered CyPep-1 was 5 mg/mL. The MTD was not reached. The CyPep-1 dose to be applied in Phase IIa Arms A, B and D is 5 mg/mL.

For cohorts 4 and 5 of Phase IIa Arm C, the doses of CyPep-1 to be investigated are 2 mg/mL and 5 mg/mL, respectively.

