5.3.6 Dose Modification

CyPep-1 dose modifications are not planned. In case of CyPep-1 related toxicity, a dose delay may be considered after review by the investigator and medical monitor.

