5.3.6.1 Dose Modifications and Management of CyPep-1 associated AEs

CyPep-1 associated hematological and non-hematological adverse effects according to CTCAE v5.0 toxicity grade may occur. Toxicity management and dose modifications are listed below:

Dose adjustments according to CTCAE toxicity grade for drug-related AEs

Occurrence	Grade 1	Grade 2	Grade 3	Grade 4
First appearance	No action with study drug.	No action with study drug.	Interrupt treatment until resolved to Grade 0-1 (or according to inclusion criteria). If interruption is < 14 days, restart at next lower dose level. If interruption is ≥14 days, check with Medical Monitor.	Discontinue study drug.

Second appearance		Discontinue study drug.	
-------------------	--	-------------------------	--

5.3.6.2 Dose modification and toxicity management for immune-related AEs associated with pembrolizumab

AEs associated with pembrolizumab exposure may represent an immunologic etiology. These immune-related AEs (irAEs) may occur shortly after the first dose or several months after the last dose of pembrolizumab treatment and may affect more than one body system simultaneously. Therefore, early recognition and initiation of treatment is critical to reduce complications. Based on existing clinical study data, most irAEs were reversible and could be managed with interruptions of pembrolizumab, administration of corticosteroids and/or other supportive care. For suspected irAEs, ensure adequate evaluation to confirm etiology or exclude other causes. Additional procedures or tests such as bronchoscopy, endoscopy, skin biopsy may be included as part of the evaluation. Based on the severity of irAEs, withhold or permanently discontinue pembrolizumab and administer corticosteroids. Dose modification and toxicity management guidelines for irAEs associated with pembrolizumab are provided in Table 3.

Table 3. Dose Modification and Toxicity Management Guidelines for Immune-related AEs Associated with Pembrolizumab

General instructions:				
irAEs	Toxicity grade (CTCAE V5.0)	Action with pembrolizumab	Corticosteroid and/or other therapies	Monitoring and follow-up

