11.1.3 Analysis

All AEs will be presented by cohort/arm and overall.

An overview table of treatment-emergent AEs (TEAEs) will be produced, including counts and percentages of subjects (n) and events (#AE) for:

1. TEAEs,
2. TEAEs related to any study treatment (CyPep-1 or pembrolizumab),
3. TEAEs related to CyPep-1,
4. Serious TEAEs (TESAEs),
5. TESAEs related to any study treatment (CyPep-1 or pembrolizumab),
6. TESAEs related to CyPep-1,
7. CTCAE grade 3 or higher TEAEs,
8. CTCAE grade 3 or higher TEAEs related to any study treatment (CyPep-1 or pembrolizumab),
9. CTCAE grade 3 or higher TEAEs related to CyPep-1,
10. TEAEs leading to any study treatment (CyPep-1 or pembrolizumab) discontinuation,
11. TEAEs leading to CyPep-1 discontinuation,
12. TEAEs leading to pembrolizumab discontinuation,
13. TEAEs related to any study treatment (CyPep-1 or pembrolizumab) leading to any study treatment discontinuation,
14. TEAEs related to CyPep-1 leading to CyPep-1 discontinuation,
15. TEAEs related to any study treatment (CyPep-1 or pembrolizumab) leading to pembrolizumab discontinuation,
16. TEAEs leading to CyPep-1 dose reduction,
17. TEAEs leading to pembrolizumab dose reduction,
18. TEAEs leading to CyPep-1 dose interruption,
19. TEAEs leading to pembrolizumab dose interruption,
20. TEAEs leading to study discontinuation,
21. TEAEs leading to study discontinuation related to any study treatment (CyPep-1 or pembrolizumab),
22. TEAEs leading to study discontinuation related to CyPep-1,
23. Dose limiting toxicities (for Phase I and Phase IIa Arms A and C),
24. Treatment limiting toxicities (only for Arm B),
25. Fatal TEAEs,
26. Fatal TEAEs related to any study treatment (CyPep-1 or pembrolizumab),
27. Fatal TEAEs related to CyPep-1.

Adverse events will be coded based on the MedDRA (version specified in the *Data Management Plan*) for reporting by SOC and PT. SOC will be ordered in accordance with the international agreed upon sort order for SOC followed by descending order of overall PT incidence within the SOC.

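### After a first drug-related Grade 3 AE with an interruption under 14 days, the protocol synopsis forbids a CyPep-1 dose reduction while Section 5.3.6.1 directs one, to a level it does not define

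*Protocol*

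**What the plan says.** Three current protocol texts govern CyPep-1 dosing after toxicity.

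- **Synopsis, dose-modification criteria.** Administration may be delayed at the investigator's discretion, with discussion with the medical monitor. Then: "Neither a dose reduction, nor intra-subject dose escalation of CyPep-1 is allowed".
- **Section 5.3.6.** Modifications are described as not planned. "In case of CyPep-1 related toxicity, a dose delay may be considered after review by the investigator and medical monitor".
- **Section 5.3.6.1, table for drug-related AEs.** At a first Grade 3 event, treatment is held until the event returns to Grade 0-1 or to the level in the inclusion criteria. "If interruption is < 14 days, restart at next lower dose level". For 14 days or more, the site checks with the Medical Monitor and no dose is named.

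Neither the prohibition nor the table is limited to a phase or arm. The table does not say what the next lower dose level is. Section 5.3.1.1 gives the Phase I concentrations as 0.5, 2 and 5 mg/mL. Section 5.3.4 sets 5 mg/mL for Arms A, B and D, and for Arm C cohorts 4 and 5 "the doses of CyPep-1 to be investigated are 2 mg/mL and 5 mg/mL, respectively".

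**The concern.** The rule fixes the dose at which a patient is re-exposed just after drug-related Grade 3 toxicity, in a first-in-human trial with safety as a primary objective. Where the interruption is under 14 days, an investigator who follows the synopsis departs from the table, and the reverse. Section 10.7 counts dosing errors with the investigational product among major deviations, yet the protocol does not settle which action would be the error.

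**Working it through.** The documents state no figure to reproduce. The check is a comparison of texts, followed by the size of the dose step.

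**1. Where the texts collide.** Take a first drug-related Grade 3 event that resolves to Grade 0-1.

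- Interruption under 14 days: the synopsis allows no reduction, so the concentration is unchanged. Section 5.3.6.1 requires the next lower level. These cannot both be followed.
- Interruption of 14 days or more: the table names no dose, so it does not contradict the synopsis.

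The conflict is confined to the first branch.

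**2. Whether other text resolves it.** Section 1.9.3 (for Arm B) refers to Section 5.3.6 for the modification rules, and Section 4.3.1 does so for toxicity requiring permanent discontinuation. Neither withdraws the synopsis sentence. Section 3.1.1 lets the Dose Escalation Committee (DEC) de-escalate in Phase IIa after reviewing safety data. That is a committee decision and not a rule for re-dosing one subject.

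**3. Size of the step at the RP2D.** Inputs: a maximum of 4 mL per treatment day (Section 5.3.1.2) and 5 mg/mL (Section 5.3.4).

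- Synopsis rule: 4 × 5 = 20 mg.
- Table, if the step is the next Phase I concentration: 4 × 2 = 8 mg, and (20 − 8)/20 = 60% lower.
- Table, if the step follows the DEC's alternative of 50-70% of the current dose level: 0.5 × 20 = 10 mg to 0.7 × 20 = 14 mg. The reduction is (20 − 14)/20 = 30% to (20 − 10)/20 = 50%.

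Both readings of the step are assumptions. The second borrows the DEC option by analogy.

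**4. Whether the branch can be reached.** Section 3.1.2 exempts from the DLT definition "Fatigue Grade ≥ 3 for ≤ 7 days". Section 5.3.5 continues treatment in the absence of a DLT or TLT. Suppose a subject at the RP2D in Arm A or C has related Grade 3 fatigue for a few days in Cycle 1, and an injection is briefly delayed. There is no DLT, dosing resumes, and the two texts give different doses. The example does not carry over unchanged to Arm B, whose TLT definition exempts Grade 3 fatigue only up to 3 days. Related Grade 3 events after Cycle 1 can also reach the rule.

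**5. Scope.** Phase I is complete, and the SAP (Section 6.1, footnote 1) reports that recruitment to Arm D stopped after one subject. That leaves Arms A, B and C as the main scope: 9 + 15 + 9 = 33 planned subjects, or 18 + 15 + 9 = 42 if Arm A is expanded.

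**The case against.** The best reply is that this is an untidy synopsis and not an open question. Two body sections send the reader to Section 5.3.6, and the grade-specific table sits there. Both delay texts also involve the medical monitor, so a site is not left to choose alone. Both points stand and make divergent practice less likely. They do not remove the synopsis prohibition, and the under-14-day cell does not itself call for consultation.

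The rule may also rarely be used. Section 5.3.4 reports related events at 5 mg/mL in Phase I as injection site pain of Grade 1 and 2, without DLTs. The synopsis omits a dose delayed more than 7 days, which narrows the under-14-day branch under two-weekly dosing, although the protocol does not say from when an interruption is counted. This limits frequency and leaves the contradiction in place.

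A reader might infer more than the documents support:

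- **That Section 5.3.6 is a second prohibition.** Its wording is permissive: modifications are not planned and a delay may be considered. The only outright ban is the synopsis sentence.
- **That the SAP sides with the table because it counts "TEAEs leading to CyPep-1 dose reduction".** Item 17 of the same list (SAP Section 11.1.3) counts reductions of pembrolizumab, for which protocol Table 3 offers only continuing, withholding or discontinuing. These look like standard action-taken rows that may be empty.
- **That Arm C cohort 4 would fall from 8 mg to 2 mg, or 75%.** This takes 0.5 mg/mL as the step, which is not a planned Arm C level. The cohort 4 step is simply undefined.
- **That results are biased.** Nothing in the documents shows this.

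**Conclusion.** The point holds, confined to a first drug-related Grade 3 AE with an interruption under 14 days. One current text forbids the reduction that another directs, and no text reconciles them or defines the step. At the RP2D the table's maximum is 30% to 60% below the synopsis rule's 20 mg per treatment day, depending on which assumption about the step is used. The number of subjects affected is unknown and may be zero, so the case for correction rests on a clear dosing instruction for patients and not on any effect on the analysis.

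**What to change.** State one rule in the same words in the synopsis, Section 5.3.6 and Section 5.3.6.1.

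- **Preferred.** Keep the Section 5.3.6.1 table. Amend the synopsis and Section 5.3.6 to allow a reduction only as that table directs. Define the step, for example 5 to 2 mg/mL, and state explicitly what applies in Arm C cohort 4. No SAP change is needed.
- **Alternative.** If reductions are to stay prohibited, delete the instruction to restart lower from Section 5.3.6.1 and say there that re-dosing is at the same concentration.

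The cost is protocol wording in three places, with no extra subjects or procedures.
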